9.5.2 Appropriateness of Measurements

All clinical assessments are standard measurements commonly used in dermatology studies as well as in the routine clinical care of patients with actinic keratosis.

9.5.3 Reporting of Serious Adverse Events, Pregnancy, and Other Events of Interest

9.5.3.1 Reporting of Serious Adverse Events

All SAEs, regardless of their relationship to study treatment, must be reported on a completed SAE form by electronic transmission as soon as possible but no later than 1 business day from the date the Investigator becomes aware of the event. SAE reporting requirements will be provided in the Investigator File.

All SAEs, regardless of causality assessment, must be collected through the last subject contact and followed to resolution or, if resolution is unlikely, to stabilization. SAEs reported to the site from the time of the last subject contact up to 30 days after the last contact, will be collected (ie, Day 57 plus 30 days). During the Recurrence Follow-up Period, all AEs, including SAEs in the treatment area will be collected until the last subject

contact. These SAEs will be discussed in the clinical study report. Any SAE event judged by the Investigator to be related to the study treatment should be reported to the Sponsor regardless of the length of time that has passed since study completion.

Deaths and life-threatening events should be reported immediately by telephone. The initial report must be submitted within 1 business day by electronically transmitting the completed SAE form.

The detailed contact information for reporting of SAEs will be provided in the Investigator File.

It is very important that the SAE report form be filled out as completely as possible at the time of the initial report. This includes the Investigator's assessment of causality. All supporting documents should be sent de-identified and should contain the assigned subject number. Only supporting documents directly related to the event should be sent.

Any follow-up information received on SAEs should be forwarded as soon as possible. If the follow-up information changes the Investigator's assessment of causality, this should also be noted on the follow-up SAE form.

Preliminary SAE reports should be followed as soon as possible by detailed descriptions including copies of hospital case reports, autopsy reports, and other documents requested by the Sponsor.

9.5.3.2 Reporting of Pregnancy

Any pregnancy, whether occurring in a subject or in the female partner of a male subject, for which the estimated date of conception was either before the last visit or within 30 days of last study treatment must be reported.

If an adverse outcome of a pregnancy is suspected to be related to study drug exposure, this should be reported regardless of the length of time that has passed since the exposure to study treatment.

A congenital anomaly, death during perinatal period, an induced abortion, or a spontaneous abortion are considered to be an SAE and should be reported in the same timeframe and in the same format as all other SAEs (see [Section 9.5.3.1](#)).

Pregnancies must be reported by electronic transmission as soon as possible but no later than 1 business day from the date the Investigator becomes aware of the pregnancy. The contact information for the reporting of pregnancies is provided in the Investigator File. The Pregnancy Report Form must be used for reporting. All pregnancies must be followed to outcome. The outcome of the pregnancy must be reported as soon as possible but no later than 1 business day from the date the Investigator becomes aware of the outcome.

A subject who becomes pregnant during the Treatment Period must be discontinued from treatment but continue to participate in the study per the protocol.

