9.1.3 Follow-up Period

After the Treatment Period for both cohorts, there will be Follow-up Visits at Days 8, 15, 29, and 57 to assess safety, activity, LSRs, pigmentation, and scarring.

For subjects who do not have complete response at Day 57, Day 57 is their Final Visit.

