9.3.1 Inclusion Criteria

Inclusion criteria will be reviewed at Screening (Visit 1).

Subjects must meet all of the following criteria to be included in this study:

1. Males and females ≥ 18 years old
2. Clinical diagnosis of stable, clinically typical actinic keratosis
3. A treatment area on the face or scalp that:
 - is a continuous area measuring 25 cm²
 - contains 4 to 8 AK lesions
4. Females must be postmenopausal (>50 years of age with at least 12 months of amenorrhea), surgically sterile (by hysterectomy, bilateral oophorectomy or tubal ligation) or otherwise incapable of pregnancy for at least 1 year; or, if of childbearing potential, must be using highly effective contraception for at least 30 days or 1 menstrual cycle, whichever is longer, prior to treatment with KX2-391 Ointment 1% and must agree to continue to use highly effective contraception for at least 90 days following their last dose of KX2-391 Ointment 1%. Highly effective contraception includes oral hormonal contraceptives, hormonal contraceptive implant or patch, or intrauterine device. Abstinence and double barrier methods do not qualify as highly effective methods of contraception.
5. Males who have not had a vasectomy must agree to use barrier contraception from Screening through 90 days after their last dose of KX2-391 Ointment 1%.
6. All subjects must agree not to donate sperm or eggs or attempt conception from Screening through 90 days following their last dose of KX2-391 Ointment 1%.
7. Females of childbearing potential must have a negative serum pregnancy test at Screening and a negative urine pregnancy test on Day 1 prior to administration of study treatment.

8. Subjects who in the judgment of the Investigator, are in good general health based on:
 - medical history
 - no physical examination (PE) findings that the Principal Investigator (PI) determines would interfere with interpretation of study results
 - screening electrocardiogram (ECG) without clinically significant abnormalities
 - clinical chemistry, hematology, and urinalysis results that are within the reference ranges; clinical laboratory values outside the reference ranges that are considered by the PI to be clinically insignificant are also acceptable
9. Willing to avoid direct sun or ultraviolet (UV) light exposure to the face or scalp
10. Able to comprehend and are willing to sign an informed consent form

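### For subjects last seen at Day 57, the mandatory pregnancy-report rule leaves out conceptions in the last 38 days (Cohort 1) or 36 days (Cohort 2) of the 90-day precaution period

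*Protocol*

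**What the plan says.** **Reporting rule.** Under Protocol 9.5.3.2, a pregnancy in a subject or in a male subject's partner falls under mandatory reporting according to its estimated conception date: one "either before the last visit or within 30 days of last study treatment must be reported". The same section adds three provisions:

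- If an adverse outcome is suspected to be related to the drug, "this should be reported regardless of the length of time that has passed since the exposure to study treatment".
- Certain outcomes are serious by definition: "A congenital anomaly, death during perinatal period, an induced abortion, or a spontaneous abortion are considered to be an SAE".
- "All pregnancies must be followed to outcome".

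**Precaution period.** Protocol 9.3.1 sets it at 90 days after the last dose. Item 4 covers women of childbearing potential. Under item 5, men without a vasectomy "must agree to use barrier contraception from Screening through 90 days after their last dose". Item 6 bars any attempt to conceive over the same period, for all subjects.

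**Last visit.** Protocol 9.1.3 states: "For subjects who do not have complete response at Day 57, Day 57 is their Final Visit". Complete responders continue to 3-monthly recurrence visits (9.1.4).

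**Other routes.** Protocol 9.5.3.1 collects SAEs whatever their cause up to last contact, and those that reach the site in the 30 days after it. Protocol 9.5.1.5.2 sends pregnancy through the SAE procedures as an event of interest. Protocol 9.5.4 provides for contact by mail, phone or other means with subjects who stop attending.

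**The concern.** The precaution period is the sponsor's own statement of how long after dosing it wants conception avoided. A conception inside it is the case the precaution was meant to prevent, so the sponsor would want to hear of it. The report rule instead depends on the last visit, which depends on response. Take two subjects with identical dosing who both conceive on Day 80. A responder who then attends the 3-month visit comes under the rule. A non-responder last seen at Day 57 does not.

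What could be lost is normal outcomes, and later adverse outcomes that nobody links to the drug. The last scheduled pregnancy test is at Day 57 (Protocol 9.5.1.5.7) and partners have no scheduled test, so after Day 57 capture rests on what subjects tell the site.

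**Working it through.** The documents state no figure for this gap, so there is none to reproduce. The check is calendar arithmetic.

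**Inputs.** Day 1 is the date of first dose (Protocol 9.7). With full dosing, the last dose L is Day 5 in Cohort 1 and Day 3 in Cohort 2 (9.1.2). The last visit V is Day 57 for non-responders (9.1.3), with a window of ±2 days (Tables 1 and 2).

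**Formulas.** Report-rule limit = later of V and L + 30. Precaution end = L + 90. Days outside the rule = precaution end − report-rule limit.

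| Case | L | V | L + 30 | Limit | L + 90 | Days outside |
|---|---|---|---|---|---|---|
| Cohort 1, all doses | 5 | 57 | 35 | 57 | 95 | 95 − 57 = 38 (42% of 90) |
| Cohort 2, all doses | 3 | 57 | 33 | 57 | 93 | 93 − 57 = 36 (40% of 90) |
| Either cohort, one dose only | 1 | 57 | 31 | 57 | 91 | 91 − 57 = 34 |
| Cohort 1, all doses, last seen by the Day 29 visit | 5 | at most 31 | 35 | 35 | 95 | 95 − 35 = 60 (67% of 90) |
| Cohort 2, all doses, last seen by the Day 29 visit | 3 | at most 31 | 33 | 33 | 93 | 93 − 33 = 60 (67% of 90) |

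The count treats Day 57 itself as covered; a strict reading of the rule would add one day. With the Day 57 visit held anywhere from Day 55 to Day 59, the first three rows become 40 to 36, 38 to 34 and 36 to 32 days. The 30-day arm adds nothing for anyone seen at Day 57, because Days 35, 33 and 31 have already passed.

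**Who has a smaller gap or none.**

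- Responders who attend the 3-month visit have none. Taking 3 months as 90 days and the earliest dates the windows allow, that visit is on Day 55 + 90 − 14 = Day 131, after Day 95.
- A further visit after Day 57 to follow a skin reaction, pigment change, scar or related AE (Protocol 9.5.1.5.1 and 9.5.1.5.8; SAP 5.5.2 and 5.5.3) moves the limit. On assumed dates, a visit on Day 71 leaves 24 days (Cohort 1) or 22 (Cohort 2), and one on Day 85 leaves 10 or 8.

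**What the SAE route reaches.** With last contact on Day 57, SAEs are collected if they reach the site by Day 57 + 30 = Day 87. For a conception after Day 57, only an early loss could occur and be reported by then. If birth comes no sooner than 22 weeks (154 days) after conception, an assumption, the earliest birth is Day 57 + 154 = Day 211. That is 124 days after Day 87, so a perinatal death or an anomaly found at birth falls outside this route unless it is judged related.

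**How many subjects.** At the planning response rate of 35% (Protocol 9.7.2), 65% of 60, or 39 evaluable subjects per cohort, would have Day 57 as their final visit. The documents do not say how many could conceive or have a fertile partner.

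**The case against.** The strongest reply is that nothing is wrong. A contraception period is a precaution and a reporting window sets a minimum for data capture. No rule in the documents says they must match, and a site may report more than the minimum. The outcomes that matter most, those suspected to be drug-related, are reportable without time limit. Protocol 9.5.1.5.2, read broadly, brings any pregnancy that reaches the site within 30 days of last contact into the SAE procedures. Protocol 9.5.4 gives the site a way to learn of pregnancies in subjects who stop attending. Final-visit instructions may already be in the consent form or Investigator File, which this review has not seen. SAP 5.2.6.1 describes doses already given, so an amendment may come too late to matter in this trial.

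Much of this stands, and it is why the point is minor. It does not remove the difference. The broad reading of 9.5.1.5.2 depends on the pregnancy being recognised and made known in time. Contact by phone or mail can move the last contact, and with it the SAE deadline, but it is not a visit and does not move the conception-date limit. The follow-to-outcome sentence reads most naturally as applying to reported pregnancies; if it covered every pregnancy, the conception-date limit would have no effect.

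Four stronger readings are tempting and not supported:

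- **That reporting stops on Day 57.** The limit is on conception date. A pregnancy conceived on Day 50 and discovered on Day 90 must still be reported.
- **That Day 87 is an alternative conception limit, leaving a gap of 8 or 6 days.** Day 87 is a deadline for news to reach the site. A conception before Day 87 is caught only if the site hears of it by then.
- **That the two sections contradict each other.** Both can be followed as written.
- **That a conception in the gap means exposure to the drug.** The documents give no washout figure, and Protocol 7.1.2 calls systemic exposure after topical use limited.

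**Conclusion.** The point holds as a minor gap in safety capture. The 38- and 36-day figures are exact for full dosing and a last visit on Day 57. They concern mainly non-responders, and also responders who attend no recurrence visit. Fully dosed subjects last seen by the Day 29 visit have 60 days outside the rule. The figures rest on the conception-date rule in 9.5.3.2 taken alone; the other routes reduce what is missed, by an amount the documents do not let one count.

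Few cases are likely. No activity endpoint, safety table or comparison of cohorts is affected; SAP 5.5.8 plans only a listing of pregnancy test results. The change is worth making because it is nearly free, not because the plan is in error.

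**What to change.** In Protocol 9.5.3.2, set the conception-date limit at the later of the last visit or 90 days after last study treatment, for subjects and for partners of male subjects, with follow-up to outcome as now. For a subject last seen at Day 57, the limit then becomes Day 95 (Cohort 1) or Day 93 (Cohort 2) and the difference is zero. Unless the consent form or Investigator File already does so, add a line to the final-visit instructions asking subjects to tell the site of any such pregnancy.

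The cost is one changed number and perhaps one added line, with no new visits or tests. The downside is a few more reports to handle, and capture still depends on subjects contacting the site. If follow-up in this trial is already over, the change belongs in the next protocol built on this text.

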9.5.3.3 Reporting of Other Events of Interest

9.5.3.3.1 REPORTING OF ADVERSE EVENTS ASSOCIATED WITH STUDY DRUG OVERDOSE, MISUSE, ABUSE, OR MEDICATION ERROR

Study drug overdose is defined as the accidental or intentional use of the drug in an amount higher than the dose being studied.

Any study drug overdose should be noted on the Study Medication CRF/eCRF.

All AEs associated with overdose, or medication error should be captured on the Adverse Event CRF/eCRF and also reported using the procedures detailed in [Section 9.5.3.1](#) even if the AEs do not meet serious criteria. If the AE associated with an overdose or medication error does not meet serious criteria, it must still be reported using the SAE form and in an expedited manner, but should be noted as nonserious on the SAE form and the Adverse Event CRF/eCRF.

9.5.3.4 Expedited Reporting

The Sponsor (or its designee) must inform Investigators and regulatory authorities of reportable events, in compliance with applicable regulatory requirements, on an expedited basis (ie, within specific timeframes). For this reason, it is imperative that sites provide complete SAE information in the manner described above.

In determining what SAEs meet criteria for expedited reporting, the current version of the Investigator's Brochure will be used for reference safety information.

9.5.3.5 Breaking the Blind

Not applicable

9.5.3.6 Regulatory Reporting of Adverse Events

Adverse events will be reported by the Sponsor or a third party acting on behalf of the Sponsor to regulatory authorities in compliance with local law and established guidance. The format of these reports will be dictated by the local and regional requirements.

9.5.4 Completion/Discontinuation of Subjects

A subject may elect to discontinue from the study at any time for any reason. See [Section 9.3.3](#) for reasons why Investigators may discontinue subjects from the study. Investigators must document the actual reason(s) why they decided to discontinue subjects, or why subjects withdrew consent, as applicable. Study disposition information will be collected on the Disposition CRF/eCRF.

Subjects who withdraw from study treatment (with the exception of death or withdrawal of consent) will be encouraged to complete the Early Termination assessments at the time of withdrawal as indicated in [Table 1](#) and [Table 2](#). A subject who has ceased to return for visits

will be followed up by mail, phone, or other means to gather information such as the reason for failure to return, the status of treatment compliance, the presence or absence of AEs, and clinical courses of signs and symptoms. This information will be recorded in the CRF/eCRF.

9.5.5 Abuse or Diversion of Study Drug

Not applicable

9.5.6 Confirmation of Medical Care by another Physician

The Investigator will instruct subjects to inform site personnel when they are planning to receive medical care by another physician. At each visit, the Investigator will ask the subject whether he/she has received medical care by another physician since the last visit or is planning to do so in the future. When the subject is going to receive medical care by another physician, the Investigator, with the consent of the subject, will inform the other physician that the subject is participating in the clinical study.

9.6 Data Quality Assurance

This study will be organized, performed, and reported in compliance with the protocol, SOPs, working practice documents, and applicable regulations and guidelines. Site audits may be made periodically by the Sponsor's or the CRO's qualified compliance auditing team, which is an independent function from the study team responsible for conduct of the study.

9.6.1 Data Collection

Data required by the protocol will be documented in the subject source documentation, collected on the CRF/eCRFs and entered into a validated data management system that is compliant with all regulatory requirements. A CRF/eCRF or a select CRF/eCRF page may be used as a source document. CRF/eCRFs used as source documents will be listed in the Data Management Plan. As defined by ICH E6 guidelines (Section 1.11), the CRF is a printed, optical, or electronic document designed to record all of the protocol-required information to be reported to the Sponsor on each study subject. In this study, the CRF may refer to either a paper (CRF) or electronic data collection form (eCRF), or both.

Data collected on the CRF/eCRF must be completed following the instructions described in the CRF/eCRF Completion Guidelines, which will be based on the Data Management Plan. The Investigator has ultimate responsibility for the collection and reporting of all clinical, safety, and laboratory data entered on the CRF/eCRF. The PI must sign the CRF/eCRF to attest to its accuracy, authenticity, and completeness.

Completed, original CRFs/eCRFs are the sole property of the Sponsor and should not be made available in any form to third parties without written permission from the Sponsor, except for authorized representatives of the Sponsor or appropriate regulatory authorities.

Responsible site personnel will enter the information required by the protocol onto the CRF/eCRFs in accordance with the CRF/eCRF Completion Guidelines that are provided. A CRA will visit each site as documented in the monitoring plan to review the CRF/eCRFs for completeness and accuracy against the source documents. They will identify any discrepancies and ensure that appropriate site personnel address the discrepancies.

The original CRFs/eCRFs will be maintained at the site in a central document repository. If used, a copy of the CRF will be forwarded to the Sponsor.

At the end of the study an electronic copy of the database along with appropriate system version will be archived.

Uniform procedures will be discussed at the Investigator meetings or at site initiation and/or will be documented in the CRF/eCRF Completion Guidelines.

9.6.2 Clinical Data Management

All data, both CRF/eCRF and external data, will be loaded into a clinical system as specified in the Data Management Plan.

Quality control and data validation procedures will be applied to ensure the validity and accuracy of the clinical data.

All software applications used in the collection of data will be properly validated following standard computer system validation that is compliant with all regulatory requirements.

9.7 Statistical Methods

All statistical analyses will be performed by the Sponsor or designee after the study is completed and the database is locked. Statistical analyses will be performed using Phoenix WinNonlin and SAS software or other validated statistical software as required.

Statistical analyses will be reported using summary tables, graphs, and data listings. Continuous variables will be summarized using the mean, standard deviation (SD), median, minimum, and maximum. Categorical variables will be summarized by counts and by percentage of subjects in corresponding categories. All raw data obtained from the CRF/eCRF, as well as any derived data will be included in data listings.

For all analyses, study Day 1 will be defined as the date of the first dose of study drug.

9.7.1 Statistical and Analytical Plans

9.7.1.1 Study Endpoints

9.7.1.1.1 PRIMARY ENDPOINTS

The primary endpoint is activity.

Activity will be evaluated by reduction in lesion count. Complete response rate will be defined as the proportion of subjects achieving 100% complete clearance of all treated AK lesions on the face or scalp at Day 57.

9.7.1.1.2 SECONDARY ENDPOINTS

Activity

Reduction in lesion counts at each visit during Days 1-57 will be assessed as the secondary endpoint for activity.

Safety

Safety will be evaluated primarily by assessment of AEs and clinical laboratory data. The results of other safety assessments (vital signs, PEs, ECGs) will also be evaluated.

Pharmacokinetic

Secondary endpoints include the following PK parameters derived by noncompartmental analysis using the plasma concentration-time data of KX2-391: C_{max} , and where applicable, AUC_t , C_{min} , and accumulation ratio R.

9.7.1.1.3 EXPLORATORY ENDPOINTS

Exploratory endpoints include recurrence and sustained response rates.

Recurrence rate will be defined as the proportion of subjects who achieved 100% complete clearance at Day 57 (Visit 10) with any identified AK lesions on the treatment area at 3, 6, 9, and 12 months post-Day 57.

Sustained response rate will be defined as the proportion of subjects who achieved 100% complete clearance at Day 57 (Visit 10) without any identified AK lesions on the treatment area at 12 months post-Day 57.

9.7.1.2 Definitions of Analysis Sets

The Per-Protocol Set is the group of protocol-eligible subjects who receive 5 days (Cohort 1) or 3 days (Cohort 2) of study treatment and complete at least one scheduled post-treatment evaluation.

The Evaluable Set is the group of subjects who receive 5 days (Cohort 1) or 3 days (Cohort 2) of treatment and complete most evaluations including the Day 57 Follow-up Visit.

The Safety Analysis/Full Analysis Set is the group of subjects who receive at least one dose of study treatment.

The PK Analysis Set is the group of subjects who receive study treatment and complete at least one scheduled post-treatment PK evaluation.

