9.4.1 Treatment Administered

Information regarding study treatment is provided in [Table 3](#).

[figure not shown]
Table 3 Treatment Administered in KX01-AK-002

Investigational Product	Strength	Size of Treatment Area	Quantity study medication/ KX2-391	Number Applications and Frequency	Study Days Administered
KX2-391 Ointment 1%	1%	25 cm ²	50 mg of study drug = 0.5 mg of KX2-391	1 application daily for 5 consecutive days (Cohort 1) or 3 consecutive days (Cohort 2)	Days 1-5 (Cohort 1) Days 1-3 (Cohort 2)

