9.7.1.7 Pharmacokinetic, Pharmacodynamic, Pharmacogenomic, and Other Biomarker Analyses

9.7.1.7.1 PHARMACOKINETIC ANALYSES

PK analyses will be performed on the PK Analysis Set.

Plasma concentrations of KX2-391 will be analyzed to determine C_{max} , and where applicable, AUC_t , C_{min} , and accumulation ratio R.

Individual timepoints will be tabulated and displayed graphically and listed for all subjects. Summary PK parameters will be analyzed as applicable.

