3 INTRODUCTION

This Statistical Analysis Plan (SAP) is based on the protocol for study KX01-AK-002 Amendment 2, v3.0, dated 26SEP2016. This SAP supersedes the statistical section of the protocol and provides data analysis details for the activity and safety data analysis in the clinical study report (CSR). It does not include information regarding the pharmacokinetic (PK) analysis of the study drug, KX2-391 Ointment 1.0%; that information is provided separately.

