5.2.6 Treatment Compliance and Extent of Exposure

5.2.6.1 Extent of Exposure

In general, subjects in each cohort at each dosing schedule received study drug in the range of 30 to 70 mg with 50 mg being the most common dose, as planned in the protocol. However, one subject from Cohort 1 and two subjects from Cohort 2 received 500 mg of study drug for each daily dose during their treatment period. In addition, dosing amount of another two subjects from Cohort 1 at Day 1 is missing because the site personnel inadvertently did not record the amount dosed after applying the study treatment on the subjects. Compared with other subjects, these overdosed or dose-missing subjects showed similar safety and activity profiles. Thus, they are still considered as protocol-eligible subjects.

The number of doses each subject received will be summarized as a continuous variable by cohort at each visit.

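### The PK Analysis Set has no condition on the amount applied, so unless the separate PK plan says otherwise it admits three subjects given 500 mg instead of 50 mg, and the summaries can then misdescribe exposure from 50 mg

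*Protocol*

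**What the plan says.** Protocol 9.7.1.2 defines the population: "The PK Analysis Set is the group of subjects who receive study treatment and complete at least one scheduled post-treatment PK evaluation". Protocol 9.7.1.7.1 then applies it: "PK analyses will be performed on the PK Analysis Set". On content, that section says that "Individual timepoints will be tabulated and displayed graphically and listed for all subjects" and that "Summary PK parameters will be analyzed as applicable". The general rule in 9.7 is "Continuous variables will be summarized using the mean, standard deviation (SD), median, minimum, and maximum". Protocol 9.7.1.1.2 names Cmax and, where applicable, AUCt, Cmin and the accumulation ratio R as secondary PK endpoints.

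The planned application, in Table 3 (protocol 9.4.1), is "50 mg of study drug = 0.5 mg of KX2-391". SAP 5.2.6.1 reports that "one subject from Cohort 1 and two subjects from Cohort 2 received 500 mg of study drug for each daily dose". It keeps these subjects as protocol-eligible because their safety and activity results resembled those of the other subjects, and it does not mention plasma exposure. The same section notes two Cohort 1 subjects whose Day 1 amount was not recorded.

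SAP section 3 says that the SAP replaces the protocol's statistical section. Of PK it says: "It does not include information regarding the pharmacokinetic (PK) analysis of the study drug"; PK is covered separately. The SAP's list of analysis sets (5.2.1) has no PK set. The separate PK document is not among the documents reviewed.

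**The concern.** The PK summaries are meant to describe systemic exposure after the studied application. The set asks only for treatment and one scheduled post-treatment PK evaluation, so a subject given ten times the planned amount qualifies like any other. Three of the five prescribed statistics (mean, SD and maximum) are sensitive to a few extreme values, and neither section provides for subjects far off the planned amount.

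No other rule in the documents deals with the three subjects. Their retention as protocol-eligible does not settle the PK question, because the PK set does not use eligibility. Compliance (SAP 5.2.6.2) counts doses, not amounts, so all three count as fully compliant if they received every dose. If they are pooled, the reported maximum could come from a 500 mg subject, and the mean and SD would describe a mixture of two amounts.

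**Working it through.** **Planned amount.** 50 mg x 1% = 0.5 mg KX2-391, and 50 mg / 25 cm² = 2 mg/cm²; both agree with the protocol. At 500 mg the figures are 5 mg and, on the same area, 20 mg/cm². The excess is tenfold.

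**Inputs from the documents.** The number at 500 mg is k = 1 in Cohort 1 and k = 2 in Cohort 2 (SAP 5.2.6.1).

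**Assumptions.**
- N = 60 or 80 PK subjects per cohort. No PK sample size is stated. About 80 is the planned enrolment per cohort and about 60 the planned Evaluable Set (protocol 9.1). The PK set is easier to enter than the Evaluable Set, so 80 is probably the nearer figure, and N = 60 gives the larger effect.
- f = exposure of a 500 mg subject relative to the others, from 1 (no difference) to 10 (proportional to amount). The documents give no dose-exposure relation; protocol 7.1.2 says only that systemic exposure after topical use is limited.
- A common between-subject CV of 50% or 100%.
- All three subjects have a post-treatment PK sample and are pooled within their cohort.

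**Mean.** Relative to the subjects at the planned amount, mean ratio = ((N - k) + k x f) / N.

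| f | Cohort 1, N=80 | Cohort 1, N=60 | Cohort 2, N=80 | Cohort 2, N=60 |
|---|---|---|---|---|
| 1 | 1.000 | 1.000 | 1.000 | 1.000 |
| 2 | 1.012 | 1.017 | 1.025 | 1.033 |
| 5 | 1.050 | 1.067 | 1.100 | 1.133 |
| 10 | 1.113 | 1.150 | 1.225 | 1.300 |

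Example (Cohort 2, N = 80, f = 10): (78 + 20)/80 = 1.225.

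**SD.** With the mean at the planned amount set to 1 and m the mean ratio, variance = [((N - k) + k x f²)(1 + CV²)/N - m²] x N/(N - 1). The SD ratio is the square root divided by CV.

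Example (Cohort 2, N = 80, f = 10, CV = 0.5): (78 + 200) x 1.25/80 = 4.344; minus 1.225² = 1.501 leaves 2.843; times 80/79 = 2.879; square root 1.697; divided by 0.5 gives 3.39.

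| f = 10 | Cohort 1, N=80 | Cohort 1, N=60 | Cohort 2, N=80 | Cohort 2, N=60 |
|---|---|---|---|---|
| CV 50% | 2.51 | 2.85 | 3.39 | 3.87 |
| CV 100% | 1.81 | 2.01 | 2.35 | 2.65 |

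At f = 2 the SD ratio is at most 1.12. At f = 1 it is 1.01, which is only the N/(N - 1) factor.

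**Day 1 pooled over cohorts.** With 3 of about 160 subjects and f = 10: (157 + 30)/160 = 1.169, a rise of about 17%.

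**What moves little.** The median, because one or two subjects in 60 to 80 barely shift the middle rank. Also R, because these subjects had 500 mg on every dosing day and the excess largely cancels within subject.

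**The case against.** The strongest reply is that the PK rules sit in a document not available here. The SAP replaces the protocol's statistical section, leaves PK out, and refers to separate PK information. That document may already deal with the three subjects. This stands: a reader might infer that the PK summaries do pool them, and the documents do not show that. They show only that the protocol's definition, followed literally, would admit them.

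A reader might also infer that the summaries are distorted. That is not shown either, because no dose-exposure relation or concentration is given. At equal exposure there is no effect, and at twofold exposure the effect on the mean is small.

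A third inference would be that the 1-versus-2 split biases a comparison of the 5-day and 3-day regimens. The documents do not support it. The regimen contrast in protocol 8.2 covers activity and safety, and 9.7.1.7.1 does not say that PK parameters are summarised by cohort. The second PK day does differ (Day 5 in Cohort 1, Day 3 in Cohort 2), so last-dose summaries would naturally separate, but no PK comparison between cohorts is planned.

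Finally, individual values are to be listed and plotted for all subjects, and the median is reported, so an extreme value would be visible. That is true, but a listing does not change what the summary table reports.

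**Conclusion.** The point holds in conditional form. The protocol's PK Analysis Set ignores the amount applied. Unless the separate PK plan provides otherwise, the three 500 mg subjects enter the summaries if they have a post-treatment PK sample, and the mean, SD and maximum of Cmax, AUCt and Cmin can then misdescribe exposure from 50 mg.

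The size runs from nothing to material, depending on an exposure multiplier the documents do not supply. The upper figures need exposure proportional to amount, and the SD figures also rest on the assumed CV. These are descriptive secondary summaries with no stated PK test. But the rule as written does admit the three subjects, so this is more than a missing detail.

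**What to change.** In protocol 9.7.1.2 and 9.7.1.7.1, and in the separate PK plan:

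- Base the main summaries of concentrations, Cmax, AUCt and Cmin on PK Analysis Set subjects other than the three who received 500 mg.
- List those three subjects' concentrations and parameters individually beside the tables.
- Give the all-subject summary as a sensitivity analysis.
- Keep the two Cohort 1 subjects with no recorded Day 1 amount in the main tables, flagged.

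An inclusion window taken from the observed amounts is not recommended, because it would be set from the data. Nor is dividing exposure by amount applied, because that assumes the proportionality the documents do not establish.

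No new data are needed. The cost is the plan wording and one extra table, and three subjects move from the main summary to a listing. If the separate PK plan already does this, only the protocol wording needs to be aligned with it.
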